4.3.3. Pharmacodynamic Biomarker Analyses

4.3.3.1. Definition of endpoint(s)

- Peripheral blood T Cell Bcl-2 expression (Data captured as Bcl-2 expression in T cells):
 - Bcl-2 expression in T cells (%)
 - Bcl-2 expression in T cells (MdFI)
 - [redacted]

4.3.3.2. Main analytical approach

It is assumed that endpoints defined in Section 4.3.3.1 are log_e normally distributed, unless distributional properties suggest otherwise.

The absolute values for the endpoints mentioned in Section 4.3.3.1 will be summarized descriptively. Line plots of the unadjusted geometric means and corresponding 95% CIs will be presented over time. Individual participant plots of the raw values over time will be presented by study intervention.

A Bayesian Mixed Model Repeated Measures (MMRM) analysis for the pooled placebo data across all cohorts and all doses of GSK3888130B will be fitted for Bcl-2 expression in T cells (MdFI) endpoint.

Non-informative priors will be used in this analysis. The prior for the regression coefficients will be normally distributed with mean 0 and a variance of 10⁶. Should there be convergence issues due to relatively small data values, the latter may be reduced to 10⁴. The variance-covariance matrix will use an inverse-Wishart prior distribution, consisting of the identity matrix and the degrees of freedom set to the number of visits included in the model. Sensitivity to changes in the degrees of freedom will be considered.

Terms in the model are specified below:

- Response: Absolute value on \log_e scale.
- Category: Study intervention, Visit.
- Interaction: Study intervention*Visit.
- Repeated: Visit.

Baseline values will be included in the response for this model, with visit = 'Baseline' and a distinct arbitrary code assigned for study intervention (the same for all baseline visits).

The following will be calculated from the model:

- For Baseline: The posterior mean for \log_e transformed Bcl-2,
- For each study intervention: The posterior means for \log_e transformed Bcl-2 for each post-baseline visit,
- For each study intervention: The posterior means for the difference from baseline for \log_e transformed Bcl-2 for each post-baseline visit,
- For each active study intervention: The posterior means for the difference from placebo for \log_e transformed Bcl-2 (GSK3888130B XX mg – Pooled placebo across cohorts) for each post-baseline visit.

These values will then be back transformed and the following presented:

- For Baseline: The posterior geometric mean,
- For each study intervention: The posterior geometric means for each post-baseline visit,
- For each study intervention: The posterior geometric means of the ratio to baseline for each post-baseline visit,
- For each active study intervention: The posterior geometric means of the ratio of each active dose to placebo for each post-baseline visit.

Equal tailed 95% credible intervals will be presented for each of the above back transformed values. In addition, the posterior probability that posterior ratios of each active dose to placebo are less than ($<$) **cci** will be calculated. A line plot of the adjusted posterior geometric means and credible intervals over time will be presented.

Dose Response Modelling

If deemed appropriate, the following dose-response models will be fitted for maximum change from baseline on a \log_e scale (Max Δ) for Bcl-2 expression in T cells (MdFI) endpoint. In order to incorporate data from both SC and IV cohorts, the estimated bioavailability will be taken into account. This bioavailability estimate will be provided by CPMS following instream PK analysis, utilising data up to and including Cohort 6 data, prior to the end of study database lock (DBL).

- Four-parameters sigmoid Emax model is defined as,

$$\text{Max } \Delta(\text{Bcl-2 expression in T cells}) = (E_o + X\beta_1) + (E_{max} + X\beta_2) * \left(\frac{dose^h}{ED_{50}^h + dose^h} \right) + \epsilon$$

- Three-parameters E_{max} model is defined as,

$$\text{Max } \Delta(\text{Bcl-2 expression in T cells}) = (E_0 + X\beta_1) + (E_{\max} + X\beta_2) * \left(\frac{\text{dose}}{ED_{50} + \text{dose}} \right) + \epsilon$$

Where -

X is the continuous baseline value of Bcl-2 expression in T cells (log_e scale),

E₀ is the minimum dose effect (placebo) (log_e scale),

E_{max} is maximum achievable effect above E₀ (log_e scale),

ED₅₀ is the dose which produces half of E_{max},

h is hill parameter determining the steepness of the dose response curve,

ε is random error assumed to be normally distributed with mean zero and constant variance (σ^2)

The final model will be selected based on the best fit to the data.

Non-informative priors will be used in the analysis. The prior for E₀, E_{max}, β_1 and β_2 will be normally distributed with mean 0 and a variance 10⁶. A functional uniform prior will be used for ED₅₀ and h (Bornkamp, 2014), where the prior density for the functional uniform prior is based on all the parameters in the model. However, if a prior distribution appears not to be truly non-informative then alternative prior distributions may be used. An inverse gamma prior with shape of 0.001 and scale of 0.001 will be used for the residual variance (σ^2).

Once the dose response model has been fitted, the posterior distribution of model parameter ED50 will be summarized through mean, standard deviation and equal-tailed 95% credible intervals and the back transformed posterior distribution of model parameters E₀ and E_{max} will be summarised through geometric means, standard deviation on log_e scale and equal-tailed 95% credible intervals.

The following will be calculated from the model:

- For each study intervention: The posterior mean for Max Δ,
- For each active study intervention: The posterior difference in Max Δ for each dose vs placebo (GSK3888130B XX mg – Pooled placebo across cohorts),

These values will then be back transformed to give:

- For each study intervention: The posterior geometric mean for the ratio to baseline (for Max Δ),
- For each active study intervention: The posterior geometric means of the ratio of each active dose to placebo.

Equal-tailed 95% credible intervals will be presented for each of the above back transformed values. The dose response curve will be plotted for the geometric mean for the ratio to baseline (for Max Δ) with 95% credible intervals. The adjusted posterior geometric means and 95% credible intervals from the Bayesian MMRM analysis will also be included on this plot.

[figure not shown]

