1.3.2. Intravenous Dosed Cohorts

Procedure	CCI	Intervention Period (Days) for IV cohorts												Notes
		1	2	3	4	5	6	7	8	9	10	11	12	
Randomization	X													
Urinalysis (Dipstick ±microscopy)		X		X	X	X	X	X	X	X	X	X		If dipstick is positive or participant has urinary symptoms send for microscopy. CCI [REDACTED]
Study Intervention Administration (IV)	X													
Discharge			X											
SARS-CoV-2 Test		<=====>												As per local guidelines.
Brief Physical Exam			X										X	
Laboratory assessments (include clinical chemistry, and haematology panels)		X		X	X	X	X	X	X	X	X	X		
CD4+ T cell counts	X				X		X	X	X	X	X	X		
CCI														
Viral quantification and serology (EBV, CMV and VZV)	X						X					X		Day 1 collection prior to administration of study intervention.
12-lead ECG	X	X	X	X	X	X	X	X	X	X	X	X		Single readings to be recorded pre-dose and at PK timepoints. Performed in triplicate if suspected clinically significant findings.
CCI														

Procedure	CCI	Intervention Period (Days) for IV cohorts													Notes
		X	X	X	X	X	X	X	X	X	X	X	X	X	
Vital signs		X	X	X	X	X	X	X	X	X	X	X	X	X	Day 1 vitals to be taken pre-dose and end of IV infusion and at CCI [REDACTED] from start of IV dosing on Day 1.
Blood collection for Pharmacokinetics		X	X	X		X	X	X	X	X		X	X		Day 1 PK samples to be collected prior to, midpoint and end of IV infusion, and at CCI [REDACTED] post-start of IV dosing.
Blood collection for Target Engagement (TE) biomarkers		X	X	X		X	X	X	X	X		X	X		Day 1 TE samples to be collected prior to and at CCI [REDACTED] post-start of IV dosing.
Blood collection for Immunogenicity		X							X		X		X	X	Day 1 collection prior to administration of study intervention
CCI			X		X		X	X		X			X		Day 1 collection prior to administration of study intervention
Blood collection for cellular biomarkers		X		X		X	X		X		X		X		Day 1 collection prior to administration of study intervention
CCI		X				X				X					Day 1 collection prior to administration of study intervention
AE Review															
SAE Review															
Concomitant medication review															

Procedure	CCI	Intervention Period (Days) for IV cohorts	Notes
CCI	CCI		

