9.4.4.2. Pharmacodynamic and Target Engagement endpoint(s)

The analyses will be based on the “PD” analysis set.

The pharmacodynamic biomarker, T Cell Bcl-2 will be analysed using a Bayesian repeated measures model, including study treatment, visit, study treatment-by-visit interactions and baseline. Non informative priors will be used for all model parameters. An inverse Wishart prior will be used for the within-subject unstructured covariance matrix. Other options may be investigated to determine an appropriate covariance structure in case of issues. If data permits, then a dose response model will be fitted. Full details of planned analysis will be specified in the SAP.

CCI

will also be analysed as specified above.

CCI

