1.2. Study Design

Overview of Study Design and Key Features					

Single Ascending Dose (SAD) design in healthy volunteers: planned IV and SC dosing in an interlocking design.
 					
Design Features	
 Phase 1, single centre, randomised, double-blind, placebo controlled, dose escalation study comprising of seven planned SAD cohorts of GSK3888130B over a range of dose levels (from ccI mg to ccI mg) in healthy participants. ccI mg IV ccI mg SC ccI mg IV. 
Participants will attend a screening visit within 28 days of study intervention. In participants who require an influenza vaccination and/or SARS-CoV-2 vaccination or booster, the screening window may be increased to 60 days.
 
Participants will receive study intervention on Day 1. For the IV cohorts, participants will remain in the unit for cc days and for the SC cohorts for cc days.
 
All participants will then attend the clinic for up to cc outpatient visits after dosing, over the course of ccI days, for safety assessments and sample collection and will receive two follow-up telephone calls; the first will be ccI days post last study visit and the second will be ccI days post last study visit. If required, additional follow-up visits may be scheduled.
				
Study intervention	
  
 Cohorts	Study Intervention	
   
 Cohort 1 – IV Dose	GSK3888130B cc mg vs Placebo	
  
	Cohorts	Study Intervention	Cohort 1 – IV Dose	GSK3888130B cc mg vs Placebo
Cohorts	Study Intervention				
Cohort 1 – IV Dose	GSK3888130B cc mg vs Placebo				

Overview of Study Design and Key Features		
	Cohort 2 – IV Dose	GSK3888130B [REDACTED] mg vs Placebo
	Cohort 3 – SC Dose	GSK3888130B [REDACTED] mg vs Placebo
	Cohort 4 – IV Dose	GSK3888130B [REDACTED] mg vs Placebo
	Cohort 5 – SC Dose	GSK3888130B [REDACTED] mg vs Placebo
	Cohort 6 – IV Dose	GSK3888130B [REDACTED] mg vs Placebo
	Cohort 7 – IV Dose	GSK3888130B [REDACTED] mg vs Placebo
Study intervention Assignment	
 The study will aim to recruit 54 participants into seven SAD cohorts. Cohort 1 and 2: Eligible participants will be randomised to receive either GSK3888130B or placebo in a 3:2 ratio comprising of five participants. Cohort 3 to 7: Eligible participants will be randomised in a 3:1 ratio comprising of eight participants, except for cohort 6 which [REDACTED] 	

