5. SAMPLE SIZE DETERMINATION

[figure not shown]
Approximately 54 participants will be recruited to seven single ascending dose cohorts. Five participants will be randomized to either GSK3888130B or placebo in 3:2 ratio in cohorts 1 and 2. Eight participants will be randomized to either GSK3888130B or placebo in 3:1 ratio in all other cohorts, **CCI**

No formal statistical techniques were used to calculate the sample size for this study; it has been determined to allow preliminary assessment of safety, tolerability, PK and PD. However, as a key secondary endpoint, considerations has been given to the ratio to baseline of the PD biomarker Bcl-2. It is assumed that this endpoint is \log_e normally distributed. Based on 6 participants from the highest GSK3888130B dosed cohort and 14 placebo participants pooled across all cohorts, the probability of different true inhibition (GSK3888130B vs. placebo) thresholds of interest is given in the table below. A non-informative prior distribution and a maximum between participant SD (\log_e scale) of 0.3 is assumed for both GSK3888130B and placebo arms.

[figure not shown]
CCI

CCI

[figure not shown]
CCI

CONFIDENTIAL

213960

CCI

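### The identity-scale inverse-Wishart prior for the Bcl-2 MMRM is called non-informative but is informative on the log scale; at the plan's SD of 0.3 it widens active-versus-placebo credible intervals by about 8% to 19%, depending on the comparator prior

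*SAP*

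**What the plan says.** SAP section 4.3.3.2 fits a Bayesian MMRM to Bcl-2 expression in T cells (MdFI). The response is the absolute value on the log_e scale. Baseline enters as a response visit with one mean shared by all groups. The section says its priors are non-informative and specifies the covariance prior as an "inverse-Wishart prior distribution, consisting of the identity matrix and the degrees of freedom set to the number of visits included in the model". The only planned check on this prior is: "Sensitivity to changes in the degrees of freedom will be considered".

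Later in the same section, for the dose-response model of maximum log-scale change in the same biomarker: "An inverse gamma prior with shape of 0.001 and scale of 0.001 will be used for the residual variance".

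SAP section 5 bases its Bcl-2 probability statements on the following: "A non-informative prior distribution and a maximum between participant SD". The SD is given as 0.3 on the log_e scale, and the endpoint there is the ratio to baseline.

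Protocol section 9.4.4.2 adds: "Other options may be investigated to determine an appropriate covariance structure in case of issues".

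**The concern.** An inverse-Wishart prior is weak or strong only relative to the scale of the data. An identity scale matrix suits variances near 1. Log-scale Bcl-2 is planned with an SD of change of at most 0.3, a variance of 0.09. The prior therefore inflates every visit variance. It adds nothing to the cross-products, so it also pulls the correlation with baseline toward zero and weakens the baseline adjustment.

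The MMRM's main outputs are affected: the 95% credible intervals for the ratio of each active dose to placebo, and the posterior probability that each ratio is below a threshold. The intervals also appear beside the dose-response fit: "The adjusted posterior geometric means and 95% credible intervals from the Bayesian MMRM analysis will also be included on this plot". They would be too wide, and probabilities for estimates beyond the threshold would be pulled toward 0.5.

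No other clause catches this. The planned sensitivity analysis leaves the scale matrix alone. The SAP sentence allowing other priors when one proves not to be non-informative belongs to the dose-response model. The protocol's allowance concerns covariance structure. The convergence checks in SAP section 4.1.2 would not flag a chain that mixes well but is over-dispersed.

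**Working it through.** The documents give no figure for the effect of this prior, and the threshold probabilities in the sample size section are redacted, so there is no plan figure to reproduce.

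**Inputs**
- N = 54 (SAP section 1.2: "The study will aim to recruit 54 participants into seven SAD cohorts"). Groups g = 8: seven active doses plus pooled placebo.
- SD of log change 0.3 (SAP section 5).
- Visits p: the day headers are redacted. The row "Blood collection for cellular biomarkers" in the IV schedule has 7 marks, and the matching SC row has 8, Day 1 pre-dose included. Assumed p = 8; other values are shown below.
- Correlation rho between visits: not given. Assumed 0.5 and 0.7.
- Complete data assumed.

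**Step 1: the prior alone.** Under IW(I, p) each visit variance is distributed as 1/chi-square(1), that is inverse-gamma(0.5, 0.5), whatever p is.
- Median SD = 1/sqrt(0.455) = 1.48.
- P(SD ≤ 0.3) = P(chi-square(1) ≥ 1/0.09 = 11.1) = 0.0009.

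**Step 2: weight against the data.** With per-visit SD 0.3 and 54 − 8 = 46 residual df, a visit's residual sum of squares is about 46 × 0.09 = 4.14. The prior adds 1.

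**Step 3: effect on the active-versus-placebo contrast.** Take one post-baseline visit and the baseline. Write IW(p, ψI) as a prior on the conditional variance given baseline and a ridge of precision ψ on the baseline slope. With flat group means, the contrast has a t posterior with N − g + 2 = 48 df and scale sum of squares ψ + RSS + b²Sψ/(S + ψ).

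At rho = 0.5 the per-visit SD equals the SD of change, so:
- RSS = 45 × 0.09 × (1 − 0.25) = 3.04
- S = 46 × 0.09 = 4.14
- expected b² = 0.25 + 0.0675/4.14 = 0.266
- ridge term at ψ = 1: 0.266 × 4.14/5.14 = 0.214

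Against the same df with vanishing scale: sqrt((3.04 + 1 + 0.214)/3.04) = 1.183, or **18% wider**.

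Against Jeffreys, which has 48 − 8 = 40 df: 1.183 × sqrt(40/48) × 2.011/2.021 = 1.07, or **7% to 8% wider**.

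**Step 4: simulation of the full model.** Gibbs sampling with p = 8, 400 to 500 data sets per setting, and an assumed split of 15 placebo and 3/3/6/6/6/9/6 active. The widening of the 95% interval under the SAP prior, as ranges over rho 0.5 and 0.7, was:

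| SD of change | vs Jeffreys | vs half-t on visit SDs | vs 0.09·I | vs 0.01·I or 0.002·I |
|---|---|---|---|---|
| 0.3 (plan's maximum) | 8% | 10% | 16–17% | 18–19% |
| 0.2 (assumed) | 24–25% | 26–27% | 31–32% | 36–38% |
| 0.15 (assumed) | 43–45% | 46% | 47–48% | 56–59% |

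The 0.002·I prior gives each visit variance an inverse-gamma scale of 0.001, the scale the SAP uses in its dose-response model.

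**Step 5: coverage and probabilities.** Actual coverage of the nominal 95% interval as written was 97.4–97.7% at SD 0.3, 98.9–99.0% at 0.2 and 99.5–99.6% at 0.15. Jeffreys gave 95.8–96.2%. Where a Jeffreys posterior gives probability 0.95, the SAP prior gave about 0.93, 0.90 and 0.87 at those three SDs.

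**Step 6: does varying the df help?** At SD 0.3 and rho 0.5, raising the df by 2 or 5 narrows the interval by only about 2% or 5%. An excess of 15.9% or 12.4% over the vanishing-scale prior remains.

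**The case against.** The strongest reply is that the size rests on choices the documents do not settle.

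- **Visits.** Counting marks under redacted headers is weak evidence. If IV and SC sampling days differ, the pooled model has more than 8 visits, some seen by one route only. The excess over Jeffreys falls to 4.7% at p = 10 and 2–3% at p = 12. This stands as a limit on that comparator: Jeffreys itself loses a degree of freedom per visit and grows wider. The 18% excess over the vanishing-scale prior does not change with p.
- **Which SD.** The prior acts on absolute visit values, while 0.3 is for change. The two coincide only at rho 0.5. At rho 0.7 the per-visit variance is 0.09/(2 × 0.3) = 0.15, the residual sum of squares is 46 × 0.15 = 6.9, and P(SD ≤ 0.39) is about 0.01. This is fair about Steps 1 and 2. It does not lower the widening, because Step 4 holds the SD of change fixed: the excess over vanishing scale is 18% at rho 0.5 and about 22% at rho 0.9. If 0.3 were the SD of absolute values, the range would be 2–12% at rho 0 and 18–30% at rho 0.7, but the SAP ties it to the ratio to baseline.
- **Comparator.** The upper figures use inverse-Wishart priors with small scales, and 0.01·I covered slightly under nominal, at about 94%. Hence the size is given as a range.
- **The dose-response prior.** It is for a different quantity with a different shape, so its scale, 500 times smaller (0.5 against 0.001), is only an illustration.
- **Consequence.** No hypothesis is tested, safety is primary, the error is conservative, and the descriptive geometric means and the dose-response fit do not use this prior. All of this stands, and it limits the severity.

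**Conclusion.** The concern holds. The prior is not non-informative for this endpoint, and nothing planned would correct it. With an SD of change of 0.3 and about 8 visits, the active-versus-placebo intervals are about 8% to 10% wider than under Jeffreys or half-t priors and 16% to 19% wider than under inverse-Wishart priors with smaller scales. Because the plan calls 0.3 a maximum, a smaller true SD would make the widening larger. The direction and mechanism are certain. The exact size depends on the visit count, the correlation, complete data and the comparator prior. It should be fixed before the final analysis, but it does not threaten the trial's primary conclusions.

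**What to change.** In SAP section 4.3.3.2, replace the identity with a scale matrix matched to log-scale Bcl-2, keeping the same df. One example from the plan's own SD is 0.09·I (0.3 squared), which gave 94.1–95.9% coverage in the simulations; since 0.09 is a change-score variance, a planning value for the per-visit variance could be used instead if one is available. Half-t priors on the visit SDs are an alternative, with 95.5–96.1% coverage.

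Extend the planned sensitivity analysis to the scale matrix as well as the df. If the identity is kept, stop describing the prior as non-informative and say that it widens the intervals.

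The cost is a line of SAP text, one model constant and an extra sensitivity run. No data or design change is needed.

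### The optional Bcl-2 Emax models use uncentred log_e baseline, so the reported E0 and Emax describe a participant with baseline MdFI of 1, not the placebo and maximum effects named in the SAP

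*SAP*

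**What the plan says.** SAP section 4.3.3.2, under Dose Response Modelling, says: "If deemed appropriate, the following dose-response models will be fitted for maximum change from baseline" on the log_e scale (Max Δ), for Bcl-2 MdFI. Both the three-parameter and the sigmoid model have the form

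Max Δ = (E0 + Xβ1) + (Emax + Xβ2)·f(dose) + ε.

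The definitions state that "X is the continuous baseline value of Bcl-2 expression in T cells" (log_e scale), that E0 "is the minimum dose effect (placebo"), and that Emax "is maximum achievable effect above" E0. The back-transformed posteriors of E0 and Emax themselves "will be summarised through geometric means", with the log_e-scale SD and 95% credible intervals. The same fit supplies a Max Δ mean for each intervention and a ratio to placebo for each dose. In addition, "The dose response curve will be plotted for the geometric mean for the ratio to baseline", with the MMRM estimates on the same plot. The baseline value at which these means, ratios and curve are evaluated is not given.

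The MMRM in the same section takes baseline as a response, with "a distinct arbitrary code assigned for study intervention (the same for all baseline visits"), so it has one common baseline mean and no baseline covariate.

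**The concern.** With an uncentred covariate, an intercept-type parameter applies at covariate value zero. Here zero on the log_e scale is a baseline MdFI of 1, and nothing in the documents suggests that participants lie near that value. A program that follows the SAP literally would report a row labelled as the placebo effect, and another labelled as the maximum effect, that are extrapolations to MdFI = 1. Those rows could carry very wide intervals and could disagree with the curve and ratios from the same fit. Because β2 is in the model, the ratio of a dose to placebo also depends on X, so the unstated evaluation baseline matters for that output too.

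**Working it through.** **Inputs.** From the SAP: the model, the definition of X, the labels, the reporting of E0 and Emax, and N(0, 10⁶) priors on E0, Emax, β1 and β2, which are too wide to pull E0 or Emax back to their mean-baseline values. Section 5 gives 54 participants, 14 pooled placebo, and "a maximum between participant SD" of 0.3 (log_e scale) for ratio to baseline. The documents give no MdFI level, baseline spread, β1, β2 or ED50, and the doses are redacted. The plan states no figure on this point to reproduce.

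**Step 1: algebra (no assumptions).** At dose 0 the mean is E0 + β1X. The full dose effect is Emax + β2X. If X is centred at its mean x̄, then

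- E0(centred) = E0 + β1·x̄
- Emax(centred) = Emax + β2·x̄

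Check on one simulated data set (median MdFI 1,000, ED50 held fixed): least-squares fitted values are identical with and without centring. Uncentred, E0 = 2.81, Emax = −3.73, β1 = −0.400, β2 = 0.451. With x̄ = 6.93, 2.81 − 0.400 × 6.93 = 0.04 and −3.73 + 0.451 × 6.93 = −0.61. These are the centred estimates.

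**Step 2: direction.** Max Δ is a post-dose value minus baseline, so noise in baseline enters with a negative sign and makes β1 negative. E0 then shifts upward when typical MdFI exceeds 1. Emax shifts only if β2 ≠ 0.

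**Step 3: assumed design for illustration.** Half-log dose spacing, ED50 at the fourth dose, true maximum ratio 0.50. Cohort 6 has 54 − 10 − 32 = 12 participants, split 9:3 by assumption, giving 39 active (3, 3, 6, 6, 6, 9, 6) and 15 placebo.

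**Step 4: precision of Emax.** The linearised model has columns 1, X, f, fX and the derivative for log ED50, with baseline log SD 0.3 and β2 = 0. SE of Emax on the log_e scale:

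| Residual SD | Centred | MdFI 3 | MdFI 100 | MdFI 1,000 |
|---|---|---|---|---|
| 0.15 | 0.055 | 0.21 | 0.85 | 1.3 |
| 0.2 | 0.074 | – | 1.13 | – |
| 0.3 | 0.110 | 0.42 | 1.71 | 2.6 |

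At MdFI 1 there is no difference. The pattern follows SE² ≈ SE²(centred) + x̄²·SE²(β2). At residual SD 0.3, SE(β2) = √(1.71² − 0.110²)/ln 100 = 1.706/4.605 = 0.371. At MdFI 1,000, √(0.110² + (6.908 × 0.371)²) = 2.6. At MdFI 3, √(0.110² + (1.099 × 0.371)²) = 0.42.

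Sensitivity at MdFI 100:

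- With 36 active and 14 placebo, the SEs are 0.90 / 1.19 / 1.81 uncentred and 0.059 / 0.078 / 0.117 centred.
- With ED50 at the third or fifth dose, the uncentred SE is 0.80 to 0.98 at residual SD 0.15 and 1.61 to 1.97 at 0.3.
- With ED50 treated as known, 36 active and 14 placebo, and residual SD 0.3, baseline log SDs of 0.2, 0.3 and 0.5 give 2.73, 1.80 and 1.10 uncentred against 0.112 centred.

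**Step 5: simulation of what would be reported.** 1,500 replicates, between-participant log SD 0.25, visit log SD 0.15, six independent post-dose visits, Max Δ the lowest log change, no placebo effect, ED50 estimated. Fitted β1 is about −0.26, β2 about 0, residual SD 0.16.

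| Quantity | Uncentred | Centred |
|---|---|---|
| exp(E0), MdFI 100 (95% range) | 2.8 (1.0 to 8.4) | 0.83 (0.77 to 0.89) |
| exp(Emax), MdFI 100 (95% range; true 0.50) | 0.07 to 3.2 | 0.44 to 0.56 |
| exp(E0), MdFI 3 | 1.1 | – |
| exp(E0), MdFI 1,000 | 5.3 | – |

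The centred 0.83 is below 1 because Max Δ takes the lowest of six visits. Closed-form check of the shift: 0.83 × 100^0.264 = 2.8.

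The shift depends on how noise divides between and within participants. With ED50 fixed at MdFI 100, between-participant SD 0.28 and visit SD 0.10 give β1 = −0.11 and exp(E0) = 1.5 against 0.88. SDs of 0.20 and 0.22 give β1 = −0.54 and 9.2 against 0.76.

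**Step 6: if β2 is not zero.** Take β1 = β2 = −0.1, MdFI 1,000, and true mean-baseline values exp(E0) = 0.95 and exp(Emax) = 0.60. The reported values would be 0.95 × 1,000^0.1 = 1.90 and 0.60 × 1,000^0.1 = 1.20. The maximum effect would appear to reverse direction.

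**The case against.** The reach is narrow. The model is optional, concerns a secondary biomarker, and tests no hypothesis. The outputs most readers will use (dose means, ratios to placebo, the curve) are sound if evaluated at the mean baseline, which is common practice. The convergence checks in SAP section 4.1.2 might expose the strong correlation between E0 and β1, and a tabulated 2.8 beside a curve starting at 0.83 would be noticed. The Output and Programming Specification, which is not among the documents, may already centre X. This limits the consequence, but none of it makes the written definition correct.

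The numerical size is wholly assumed, and this stands. The 0.3 in section 5 is a maximum for ratio to baseline. It supports neither the baseline spread nor, directly, the residual SD of Max Δ, which is an extreme over visits. The uncentred SE falls as baseline spread rises.

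Two qualifications also stand. All calculations are least-squares. The SAP's functional uniform prior for ED50 and h involves all model parameters, so a minor effect on ED50 through the prior cannot be excluded. And centring does not make the curve and the MMRM estimates the same quantity: the MMRM gives visit-wise means, while Max Δ is each participant's extreme.

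**Conclusion.** The concern holds. As written, E0 and Emax are values at baseline MdFI = 1 and do not carry the meaning the SAP assigns them, unless typical MdFI is near 1 or, for the point values only, the relevant slope is zero. This rests on algebra alone. The size is conditional on the assumed MdFI level, spread and slopes: negligible at MdFI 1, modest at 3, and large at 100 or above, where the SE of Emax is roughly 15 times the centred value (0.85/0.055). Least-squares fitted values and ED50 do not change, and the MMRM is not involved. Because the analysis is optional and descriptive, this is a low-priority clarification, worth making because it costs so little.

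**What to change.** In SAP section 4.3.3.2, define X as log_e baseline minus the overall mean log_e baseline of the participants in the model. Alternatively, keep X and report E0 + β1·mean(X) and Emax + β2·mean(X) in place of E0 and Emax. Add that the Max Δ means, the ratios to placebo and the plotted curve are evaluated at that mean baseline. This also gives the curve a stated baseline to set beside the common baseline mean of the MMRM, though the two still estimate different quantities. The cost is one sentence in the SAP and one line of code. If the programming specification already centres X, the sentence only documents it.
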